8.1 Study Endpoints

Primary endpoint: immediately upon removal of Tegaderm™ and EyeGard®

Secondary endpoint: post-operative day 1 when patient satisfaction data is acquired

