2.4 Alternatives

The alternative is not participating in the study.

3 Objectives

This objective of this study is to compare the effects of Tegaderm™ vs. EyeGard® on the eyelids during anesthesia.

- Primary Outcome:
 - The proportion of eyelids with erythema at the end of surgery after removal of Tegaderm™ vs. EyeGard®
- Secondary Outcomes:
 - Patient Satisfaction
 - Rate of Corneal Abrasions

4 Enrollment and Withdrawal

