5.1 Study Timelines

- Study subjects will be participating in the study for a total of 2 days.
- On day 1, study subjects will enroll in the study and undergo anesthesia with application of Tegaderm™ and EyeGard® on the eyelids. Once surgery is complete, the Tegaderm™ and EyeGard® will be removed and photograph will be taken. This will conclude participation in the study on day 1
- On day 2, study subjects will be approached by the co-investigator, [name], and will be given a patient satisfaction survey. Completion of the survey will conclude study subject participation in the study.
- We anticipate that we will be able to enroll 5 subjects per day during weekdays. Given that we plan to recruit 159 study subjects, it will take approximately 2 months to enroll all the study subjects.
- The estimated date for primary analyses will be October-December 2018.

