On post-op day 1, the co-investigator, [name], will administer a patient satisfaction survey. Once the survey is collected, the subject's participation in the study will cease.

All photographs will be uploaded to a hospital-provided Box.com account. Photograph files will be named in the following format: "001pre.xxx" or "001post.xxx," such that the "001" portion indicates study subject number, and the "pre" or "post" indicates when the photograph was taken ("pre" indicates that the photograph was taken prior to application of the EyeGard®/Tegaderm™, post indicates that the photograph was taken after removal of the EyeGard®/Tegaderm™). The "xxx" indicates the file format in which the photograph is saved.

The Box.com folder containing the photographs will be shared with the dermatologists who will evaluate the degree of erythema. The dermatologists will be asked to evaluate the erythema based on the following tape-associated skin index grading scale:

Erythema assessment:

0 - no visible erythema

1 - mild erythema

2 - moderate erythema

3 - severe erythema

Each dermatologist will be given a "Dermatologist Evaluation Sheet" which will list all of the photographs that are to be evaluated. He or she will independently evaluate each photograph.

Once all dermatological evaluations of the photographs are complete, the results will be compared. Should there be inconsistency in the Grade rating, the majority (two out of three) will be counted.

If the EyeGard® and/or Tegaderm™ fall off prior to the end of surgery, a photograph will be taken at that time and the time duration noted. Afterwards, a new tape will be re-applied.

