7.2 Reporting Procedures

Patients are routinely monitored for development of adverse events as part of their anesthetic care. This occurs on a continuous basis from the moment the anesthetic is administered until the moment the patient is

discharged home. A computerized system exists which alerts clinicians to the development of some adverse effects, and is recorded in the medical record. The co-investigator, [name], will be alerted in these situations and all adverse events will be forwarded to the principal investigator. Clinicians are alerted to events immediately as they occur. Clinical staff are trained to deal with such events. The co-investigator, [name], will be responsible for contacting the principal investigator to report the occurrence of adverse events. The principal investigator will then complete any necessary safety forms, include the Anesthesia Department's Quality Assurance form. The events will be reported within 24 hours to the QI director and the Chairman of the department, and to the IRB within 5 days.

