8.2 Statistical Analysis

We will convert our Grading Scale into a binary variable where 0 indicates no erythema and 1 indicates any erythema. The difference in erythema between Tegaderm™ vs. EyeGard® will be compared using the McNemar test.

Secondary outcomes:

1. Aggregate patient satisfaction score, is on a Likert scale from 0-5. The mean for each group (Tegaderm™ vs. EyeGard®) will be calculated and then the difference between the two groups will be determined using Student's *t*-test.

2. Corneal abrasion rate

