8.4 Data Management

The data to be collected will be divided into two general groups: (1) Paper forms, such as the consent forms and data collection sheets, will be stored in the principal investigator's locked office. (2) Digital form, such as the data collection excel spreadsheet which includes the following variables: Subject ID, R and L eye tape assignments, length of surgery, R and L eye pre-op photo numbers, R and L eye pre-op scores (from three dermatologists), R and L eye post-op photo numbers, R and L eye post-op scores (from three dermatologists), final erythema score (post minus pre), patient satisfaction with R eyelid condition, patient satisfaction with L eye condition, and additional notes, will be stored on a Tufts Medical Center provided, password protected, encrypted, Box storage account, which is compliant with institutional policies regarding HIPAA and the IT department. (3) All photos will also be stored on Box.com.

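### Corneal abrasion rate is a secondary outcome, but no described procedure looks for it and no listed variable records it by eye, so a low or zero count by tape would be hard to interpret

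*Combined protocol and SAP*

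**What the plan says.** Section 3 lists "Rate of Corneal Abrasions" among the secondary outcomes. Section 8.2 repeats it as "Corneal abrasion rate", with no definition, assessor, test or interval. Section 8.1 gives one secondary time point: "Secondary endpoint: post-operative day 1 when patient satisfaction data is acquired".

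Sections 5.1 and 5.2 describe what is done to each patient: photographs of the closed eyelids before taping and after removal, erythema grading of those photographs by dermatologists, and a survey. On the last of these: "On post-op day 1, the co-investigator, [name], will administer a patient satisfaction survey". Follow-up then stops: "Once the survey is collected, the subject's participation in the study will cease".

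Section 8.4 lists the spreadsheet variables. Tape assignment, photograph numbers, erythema scores and satisfaction are held by eye, and the list closes with "patient satisfaction with R eyelid condition, patient satisfaction with L eye condition, and additional notes". Corneal abrasion is not on it.

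Section 7.2 relies on routine clinical monitoring for adverse events: "This occurs on a continuous basis from the moment the anesthetic is administered until the moment the patient is" sent home. It says the computerized alerts pick up some adverse effects. Events go to the principal investigator, department quality staff and the IRB.

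**The concern.** Closed-lid photographs cannot show the cornea, and the survey is described only as a measure of satisfaction. Nothing in the described conduct of the study therefore asks whether an abrasion occurred. What remains is whatever clinical staff happen to notice and chart.

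The within-patient design makes this worse. Every patient receives both products, one on each eye, so an abrasion contributes to the comparison only if its side is recorded. An abrasion noted without a side counts for neither tape.

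A missing test can be chosen before analysis, but incomplete ascertainment cannot be repaired then. If the report shows few or no abrasions, a reader could not tell whether they were rare or were not looked for. That matters because Section 2.1 already takes it as given that these products lower corneal abrasion risk, so a passive zero could look like confirmation.

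**Working it through.** **1. The plan's own figure.** Section 8.3 gives 144 patients (288 eyes) for erythema at 50% vs 33%, alpha 0.05 and power 80%. With independent eyes, the discordant probabilities are 0.50 × 0.67 = 0.335 and 0.33 × 0.50 = 0.165. An exact two-sided McNemar test then needs 143 pairs, and power at 144 is 0.804, so the figure reproduces. The target of 159 is 144 × 1.10 = 158.4, rounded up. This calculation covers erythema only; the documents give no abrasion rate.

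**2. Where could an abrasion be recorded?**

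| Source | Looks for corneal abrasion? | By eye? |
|---|---|---|
| Photographs (5.2) | No, closed lids graded for erythema | Yes |
| Day-1 survey (5.1, 5.2, 8.4) | Not described; satisfaction only | Yes, for satisfaction |
| Listed variables (8.4) | No field; free-text notes only | Not structured |
| Adverse events (7.1, 7.2) | Passively; an abrasion is mentioned but not called corneal | Not stated |

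**3. What a zero would mean with complete ascertainment.** The two-sided 95% Clopper-Pearson upper limit for 0/144 is 1 − 0.025^(1/144) = 2.53% per tape. The one-sided 95% limit is 1 − 0.05^(1/144) = 2.06%.

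**4. What a zero would mean with partial ascertainment.** Let s be the share of true abrasions that reach the data with a side. The documents give no value, so s is an assumption. The two-sided limit on the true rate becomes 2.53%/s: about 5.1% at s = 0.5 and about 25% at s = 0.1.

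The chance of recording none in 288 eyes, with independent eyes and a true rate p for both tapes, is (1 − ps)^288. For an assumed p of 1%:

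- s = 1: 0.99^288 = 5.5%
- s = 0.5: 0.995^288 = 24%
- s = 0.1: 0.999^288 = 75%

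The same true rate could therefore produce a clean zero rarely or most of the time, depending on a quantity the plan does not control.

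**5. What a paired test could show.** With m discordant patients all in one direction, the exact two-sided McNemar p-value is 2 × 0.5^m. For m = 5 it is 0.0625 and for m = 6 it is 0.031. At least 6 are needed, which is 6/144 = 4.2% of patients.

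Exact power at 144 pairs, with full ascertainment, independent eyes and assumed rates:

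| Rates by tape | Power |
|---|---|
| 1% vs 0.1% | 0.3% |
| 2% vs 1% | 2% |
| 2% vs 0.5% | 4% |
| 5% vs 2.5% | 12% |
| 5% vs 1% | 38% |

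**The case against.** The strongest reply is that the documents do not show abrasion data will be absent. Much of it stands.

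- Section 8.4 introduces its variables as included, not as a complete list. It omits the baseline demographic and clinical data that Section 5.2 says will be gathered, and it ends with a free-text field. The survey and the paper data sheet are not reproduced, so either might ask about the eyes.
- The adverse-event definition in Section 7.1 is broad enough to cover an abrasion, and Section 7.2 forwards all events to the principal investigator. Since tape assignment is held by eye, a charted abrasion with a recorded side could be linked to its tape.
- Contact does not end at discharge. Sections 5.1 and 5.2 describe a day-1 contact, and Section 10.1 has patients followed to post-operative day 1. Section 8.1 could also be read as setting day 1 for all secondary outcomes.
- The plan proposes no test or comparative claim for abrasion, and its hypothesis and sample size concern erythema alone.

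These points rule out stronger readings that a reader might infer: that nothing can be recorded, that a false zero is certain, or that the cornea goes unobserved once the patient leaves. They do not supply an assessment method. A route that depends on an unprompted complaint, a chart entry and a noted side is not ascertainment of a named outcome.

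**Conclusion.** The point holds as a gap in ascertainment. Following the described procedures would probably give an incomplete abrasion count that cannot be reliably assigned to a tape, and a low or zero count would be hard to interpret. The consequence is confined to one secondary outcome; the primary erythema comparison and its sample size are untouched. It should be corrected, but it does not threaten the trial's main conclusion.

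The figures 2.5% and 6 discordant patients need only 144 complete pairs. The power values and the chances of a zero rest on assumed rates, assumed shares recorded and independent eyes. A reader might infer from them that abrasion can only ever be descriptive here. That would require a known low rate, which the documents do not give. Descriptive reporting is advisable because power is weak across the range shown, not because a comparison is impossible.

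The conclusion also assumes that the unreproduced survey and data sheet contain no abrasion item. If they do, Sections 5.2 and 8.4 need only say so.

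**What to change.** Either of two changes resolves this.

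**Keep it as a secondary outcome.**
- Add separate right-eye and left-eye fields to Section 8.4 for (a) corneal abrasion documented in the chart or an adverse-event report, and (b) eye pain or foreign-body sensation asked at the existing day-1 contact. Keep (a) and (b) apart; a symptom must not be coded as an abrasion.
- State the method and the window in Sections 5.2 and 8.1. Reconcile Section 7.2, where monitoring ends at discharge, with Section 10.1, where follow-up runs to post-operative day 1.
- In Section 8.2, specify paired counts by tape with exact 95% confidence intervals, labelled descriptive.

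**Or drop it.** Remove corneal abrasion from Sections 3 and 8.2 and report it only as an adverse event.

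The first option costs a few spreadsheet fields, one or two questions and a small amendment needing IRB approval (Section 10.4). Sample size, randomization and the primary analysis do not change. Its limitation is that chart and symptom ascertainment may miss mild abrasions, which the report should say.

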8.2 Statistical Analysis

We will convert our Grading Scale into a binary variable where 0 indicates no erythema and 1 indicates any erythema. The difference in erythema between Tegaderm™ vs. EyeGard® will be compared using the McNemar test.

Secondary outcomes:

1. Aggregate patient satisfaction score, is on a Likert scale from 0-5. The mean for each group (Tegaderm™ vs. EyeGard®) will be calculated and then the difference between the two groups will be determined using Student's *t*-test.

2. Corneal abrasion rate

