8.3 Number of Subjects

A previous study by Zeng et al. found that the rate of any level of eyelid erythema when using 3M Medipore is 50% while when using 3M Kind Removal Silicone Tape is 33%. We will assume that the rate of erythema with 3M Tegaderm may be similar to that of 3M Medipore and the rate of erythema with EyeGard may be similar to that of 3M Kind Removal Silicone Tape. Given that we are doing a study of matched pairs of subjects (the same study subject will undergo both treatments, one on each eye), the McNemar test is most appropriate. In order to detect a difference in erythema rates with an alpha of 0.05 and 80% power, G*Power determined that the total sample size needs to be 288 eyes, which is 144 patients. In order to account for a 10% attrition rate, we will plan on recruiting 159 study subjects.

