8.5 Randomization

Will subjects be randomized?

Yes No

In order to randomly allocate study subjects to one of three arms entirely by chance, we will use the on-line randomization tool "Research Randomizer Version 4.0, www.randomizer.org," which is a computer-based "random number generators," the numbers are generated by use of a complex algorithm (seeded by the computer's clock) that gives the appearance of randomness. This tool has been studied and validated as an adequate randomization tool, to generate a randomization list. Allocation concealment will be maintained by preparing sequentially numbered, sealed, opaque envelopes, which will contain the randomization assignment consistent with the generated randomization list.

The following strategies will be implemented in order to ensure blinding:

- (a) When a subject enrolls in the study, the co-investigator, [name], will open the envelope with randomization number inside. [name] will be the one to apply and remove the tapes. Once the tapes are removed, a second set of photographs will be taken. The dermatologists who will be in charge of determining the primary outcome (erythema score) will not be present during any part of the procedure.
- (b) The photos will only be linked to the experimental variable (tape type) by the data collection spreadsheet that is only accessible to the principal investigator, [name], and the co-investigator, [name]. After data collection for the study is complete, the photos will be presented to the dermatologists independently in a blinded manner.
- (c) Each dermatologist's grading will subsequently be recorded in the data collection spreadsheet by the co-investigator. Therefore, the dermatologist will have no opportunity to determine the type of tape used at any point during the study.
- (d) Study subjects will not be informed of which tape is assigned to which eyes, and the tape will be applied and removed while the patient is under anesthesia. Therefore, the patient will be blind to the type of tape used throughout the course of the study, including when he/she is reporting his/her satisfaction with post-operative eyelid condition.

9 Drugs or Devices

Will the research involve drugs?

Yes No

Will the research involve devices?

Yes No

10 Study Administration

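### Does section 8.2 leave open whether the McNemar test uses the post-removal grade or the change from baseline?

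*Combined protocol and SAP*

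**What the plan says.** Section 3 (Objectives) gives the primary outcome as "The proportion of eyelids with erythema at the end of surgery after removal of Tegaderm™ vs. EyeGard". Section 8.1 fixes the time: "Primary endpoint: immediately upon removal of Tegaderm™ and EyeGard". Section 8.2 supplies the coding, "We will convert our Grading Scale into a binary variable where 0 indicates no erythema and 1 indicates any erythema", and names the McNemar test for the comparison of tapes. The scale itself is in section 5.2: grades 0 to 3, given independently by three dermatologists to each listed photograph, with the rule "Should there be inconsistency in the Grade rating, the majority (two out of three) will be counted".

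The spreadsheet described in section 8.4 holds pre-operative and post-operative scores for each eye, and also a "final erythema score (post minus pre" value. That value appears nowhere else. The same list includes "R and L eye tape assignments, length of surgery", and section 8.5 says each dermatologist's "grading will subsequently be recorded in the data collection spreadsheet by the co-investigator". Section 4.2 excludes patients with pre-existing eyelid erythema.

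**The concern.** Section 8.2 does not say which photograph supplies the grade. The scale is applied before and after taping, and a column labelled as the final score is a difference from baseline. An analyst working from the spreadsheet alone might take that column as the primary variable. A lid graded 1 before and 1 after is erythema on the post-removal grade but 0 on the change score, and no rule covers negative changes. The person entering the grades can also see the tape assignments, so a choice made at that stage would not be blinded.

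The order of the majority rule and the dichotomy is also unstated. When the three dermatologists give three different grades, no grade has two votes. At stake would be two analysts reaching different primary results, or a small rise in the false-positive rate if the definition were chosen after seeing the results.

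**Working it through.** **1. The plan's own figure.** Section 8.3 bases the sample size on "the rate of any level of eyelid erythema when using 3M Medipore is 50" per cent, against 33% for the comparator tape. The within-patient correlation is not given; I take the two eyes as independent.
- Discordant probabilities: 0.50 × 0.67 = 0.335 and 0.33 × 0.50 = 0.165, total 0.50.
- Exact two-sided McNemar test, α = 0.05: 143 pairs are needed for 80% power, and power at 144 pairs is 80.4%. The plan's 144 is reproduced.
- Attrition: 144 × 1.1 = 158.4, rounded up to 159, as stated.

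Naming the input variable alters none of these inputs.

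**2. Which variable does the text select?**

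| Source | Pre-operative grade | Post-removal grade | Post minus pre |
|---|---|---|---|
| Section 3: erythema after removal | no | yes | no; it measures worsening |
| Section 8.1: at removal | no | yes | only in part; it also needs baseline |
| Section 8.2: tapes compared | no; taken before taping | yes | yes |
| Section 8.2: 0 means no erythema | yes | yes | no; 1 − 1 = 0 with erythema present |
| Scale in section 5.2: 0 to 3 | yes | yes | no; −3 to +3 |

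Only the post-removal grade satisfies every line.

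**3. How far could the other reading move the result?** The documents give no rate of non-zero baseline grades, so let *b* be an assumed fraction of lids graded 1 or more at baseline. At *b* = 0 the two variables are identical. Take first real redness in both eyes, persisting after removal, at *b* = 5%:
- Post-removal rates: 0.05 + 0.95 × 0.50 = 52.5% and 0.05 + 0.95 × 0.33 = 36.3%. Power is 78.3%.
- Change score: 78.3% if red lids never register as worse, 80.4% if they do so as often as clear lids redden.

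The wider range below comes from simulation at 144 pairs with the exact test. Baseline grades reflect either real redness or grading noise, and occur in both eyes together or independently. The first result column uses 50% versus 33%. The second uses 40% for both tapes and reports whichever definition is significant.

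| *b* | Definitions disagree on p ≤ 0.05 | False-positive rate, at most |
|---|---|---|
| 1% | 0–4.5% | 4.5% |
| 2% | 0–6.7% | 4.8% |
| 5% | 0–11.2% | 5.4% |
| 10% | 0–17.1% | 6.0% |

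Either definition used alone has a false-positive rate of 3.8%. The upper ends come from one corner of the grid: real redness arising independently in each lid, with no red lid ever counted as worse. When real redness affects both eyes, the largest disagreement is about 1.9%, 3.0%, 5.4% and 8.3%, and the largest false-positive rate about 4.1%, 4.3%, 4.6% and 5.0%.

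**4. The majority rule.** Three dermatologists and four grades give 4³ = 64 ordered triples. Those with three different grades number 4 × 3 × 2 = 24. At most one of three different grades can be 0, so each of the 24 has at least two non-zero grades and codes as any erythema. In the other 40, at least two grades agree and the binary value is the same whichever step comes first. The order therefore cannot alter the primary variable. The count of 24 is of possible combinations, not an expected frequency.

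**The case for a change.** The best case for a change is that pre-specification should not rely on inference. The change score is labelled as final, a baseline photograph is taken for each patient, and the dermatologists grade only after data collection, so they may see redness that was missed at enrolment. Assignments and grades share a spreadsheet. With the uncorrected chi-square form of the test (5.0% alone), picking the better of the two definitions could raise the false-positive rate to 6.3% at *b* = 2% and 7.8% at *b* = 10%. Two sentences would close the matter at almost no cost.

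Parts of this stand: section 8.2 does not repeat the time point, and the change score has no stated role. But a column in a data-management list is not a rival endpoint; the length of surgery is listed there too and has no analysis attached. The false-positive figures need someone to set aside the outcome named in section 3 and choose by result, and nothing in the plan provides for that. The plan does not say who analyses the data, and the grading itself is blinded. The larger values of *b* have no support in the documents and sit badly with the exclusion of pre-existing erythema.

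**Conclusion.** The concern does not call for a change. Read together, sections 3, 8.1 and 8.2 make the primary variable any erythema on the post-removal photograph, and an analyst following them would use it. What remains is a wording gap: a time point not repeated and a derived column without a label. Neither definition alone favours a tape or inflates the type I error, and the effect on power can go either way. With *b* at 2% or less and the exact test, even deliberate selection keeps the false-positive rate below 5%. The sizes rest on assumed baseline rates, independent tape effects and 144 analysed pairs; the reading of the text and the majority-rule count need none of these. If the investigators wish to tidy the text before grading, they could name the post-removal grade in section 8.2 and label the change score as descriptive. That would record the existing plan and leave the outcome, test, sample size and conclusion as they are.

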Enrollment	Randomization	Arm 1	159 patients	Tegaderm™ on R eye, EyeGard® on L eye
		Arm 2	159 patients	Tegaderm™ on L eye, EyeGard® on R eye

2. Introduction

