5.2 Procedures

- Is there a placebo control arm?

Yes No

We will perform a prospective, double-blind, randomized controlled trial. Participants will be approached by the co-investigator, [name], on the day of the surgery. The research study will be explained and potential participants will be given an informed consent form to read. After the participant has had adequate time to read through the informed consent form, think about the risks and benefits, and ask questions, he or she will be asked to sign the form if he or she wishes to participate in the study. The informed consent form will then be stored in the principal investigator's locked office. Once a study subject is enrolled, the anesthesia provider, surgical provider, as well as the nurse will be informed that this participant is part of the study. The co-investigator, [name], will then gather baseline patient demographic and clinical data.

Photographs will be taken using a digital camera at an angle parallel to the eyes (such that the camera is facing the patient directly), at a distance of 6 inches from the eyes to the lens of the camera, and will be done in the operating room with all room lights on. The photographs will be taken and cropped in such a way that both eyelids are visible but no other facial features will be recognizable. As such, photographs will not be identifiable. A disposable paper ruler will be used to determine camera distance and then placed on the patient's forehead during photography as a marker of size.

Upon entry into the operating room and prior to induction of anesthesia and prior to administering oxygen, the co-investigator, [name], will ask the study subject to close his or her eyes. The co-investigator will then take a photograph of the eyelids as a baseline assessment. Afterwards, anesthesia will be induced according to standard of care at Tufts Medical Center. Once the anesthesia provider establishes mask ventilation, the co-investigator, [name], will apply the EyeGard® on one eye and the Tegaderm™ on the other eye according to the

randomization schema. The exact time of application will be documented. At the end of the surgery, the co-investigator, [name], will remove the EyeGard® and Tegaderm™. She will then take another photograph of the eyelids and document the time.

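### The satisfaction comparison is worded as a two-group Student's t-test with no pairing specified, although every patient wears both tapes and scores both eyes

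*Combined protocol and SAP*

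**What the plan says.** **Design.** Under section 5.2 the co-investigator "will apply the EyeGard® on one eye and the Tegaderm™ on the other eye". The enrollment schema shows what is randomized: which eye receives which tape (Arm 1 is "Tegaderm™ on R eye, EyeGard® on L eye"; Arm 2 is the reverse). Section 8.3 states that "the same study subject will undergo both treatments, one on each eye".

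**Data.** The spreadsheet in section 8.4 holds, for each subject ID, the tape assigned to each eye and "patient satisfaction with R eyelid condition, patient satisfaction with L eye condition".

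**Analysis of erythema.** Section 8.2 names a paired test: "The difference in erythema between Tegaderm™ vs. EyeGard® will be compared using the McNemar test". Section 8.3 justifies that choice by the matched pairs.

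**Analysis of satisfaction.** Section 8.2 introduces the outcome with "Aggregate patient satisfaction score, is on a Likert scale from 0-5" and continues: "The mean for each group (Tegaderm™ vs. EyeGard®) will be calculated and then the difference between the two groups will be determined using Student's" *t*-test. It does not mention pairing, a within-patient difference or a difference score, and no other section adds this.

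**The concern.** The Tegaderm and EyeGard groups are two eyes of the same patients, rated by the same respondent. Computing a mean for each group and then testing between the groups describes the independent-samples procedure, and an analyst who follows section 8.2 literally would run it. That procedure takes the variance of the difference to be the sum of two independent variances. Scores from one person on one survey are likely to be correlated, so the standard error, confidence interval and p-value would not fit the design.

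The plan recognises the pairing for erythema and does not carry it over to satisfaction. It therefore leaves open two tests that give different p-values from the same data. The background in section 2.1 gives patient satisfaction as a reason why eyelid irritation matters, so a real difference in satisfaction could be missed for want of precision that the design already provides.

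The word *aggregate* adds some uncertainty. It could mean a composite of survey items for each eye, or pooling across patients.

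**Working it through.** **Figures in the plan.** Section 8.3 gives 144 patients (288 eyes) for the McNemar comparison. This reproduces: with erythema rates of 50% and 33% and independence between eyes assumed, the discordant proportion is 0.50 × 0.67 + 0.50 × 0.33 = 0.50, and exact two-sided McNemar power at 144 pairs is 0.804. For satisfaction the plan states no SD, expected difference, correlation or power, so there is no figure to reproduce.

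**Inputs.** n = 144 pairs (section 8.3). Assumed: equal SDs in the two eyes, SD = 1 point where a point scale is needed, normal scores, and r = 0.3, 0.5 or 0.7. Values of 0 and −0.3 are shown for contrast.

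**Step 1, standard errors.**
- Two-sample: SD × √(2/n)
- Paired: SD × √(2(1 − r)/n)
- Ratio, two-sample to paired: 1/√(1 − r), whatever n is. This is 1.20, 1.41 and 1.83 at r = 0.3, 0.5 and 0.7.

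**Step 2, 95% confidence interval half-width with SD = 1.**
- Two-sample, 286 df: 1.968 × √(2/144) = 1.968 × 0.1179 = 0.232
- Paired, 143 df, r = 0.3: 1.977 × √(1.4/144) = 1.977 × 0.0986 = 0.195
- Paired, r = 0.5: 1.977 × √(1.0/144) = 1.977 × 0.0833 = 0.165
- Paired, r = 0.7: 1.977 × √(0.6/144) = 1.977 × 0.0645 = 0.128

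**Step 3, true type I error of the two-sample test at nominal two-sided 5%.** The rejection probability is approximately 2 × P(Z > 1.968/√(1 − r)). This gives 1.86%, 0.54% and 0.03% at r = 0.3, 0.5 and 0.7. The approximation treats the pooled variance as known. Allowing for its estimation raises the values slightly, to those in the table.

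**Step 4, power for an assumed difference of 0.2 SD with 144 pairs.** This sets the two tests side by side on the same data.

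| r (assumed) | SE ratio | Paired half-width (two-sample 0.232) | Type I error, two-sample | Power, two-sample | Power, paired |
|---|---|---|---|---|---|
| −0.3 | 0.88 | 0.266 | 8.5% | 41% | 32% |
| 0 | 1.00 | 0.233 | 5.0% | 39% | 39% |
| 0.3 | 1.20 | 0.195 | 1.9% | 37% | 52% |
| 0.5 | 1.41 | 0.165 | 0.6% | 35% | 66% |
| 0.7 | 1.83 | 0.128 | 0.04% | 31% | 87% |

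The estimated mean difference is the same under both tests when both scores are present. Only its stated uncertainty changes.

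**The case against.** The strongest reply is that this is loose wording, not an error. *Student's t-test* includes the paired form. A mean paired difference equals the difference of the two means when both scores are present, so reporting a mean for each tape is compatible with a paired test. Section 2.1 also speaks of two groups when it states the erythema hypothesis, and that comparison is analysed with McNemar, so the word *group* does not by itself signal an unpaired analysis here. Section 8.3 describes the study as one of matched pairs, and the spreadsheet keeps both scores together, so a statistician could run the paired test without an amendment.

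Much of this stands: it cannot be said that an unpaired test will be run. But section 8.3 draws its matched-pairs conclusion for McNemar only, and section 8.2 leaves the satisfaction test open. An analysis section should settle that choice before the data are seen.

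It is also fair that the sizes rest on assumed values and that normal theory is an approximation for a bounded 0–5 score. A negative r is possible, for example if patients rate one eye against the other. The two-sample test would then be anti-conservative (about 8.5% at r = −0.3), and the paired test would still be the right one.

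**Conclusion.** The concern holds. Section 8.2 does not specify pairing for satisfaction, and its wording points towards a two-sample test that does not match the within-patient design. Run that way, with positive r between 0.3 and 0.7 and equal SDs, the standard error is 20% to 83% too large. With 144 pairs the true type I error falls from 5% to between about 1.9% and 0.04%. The test is conservative in that range, so the cost is lost precision and power. At r = 0 the two tests nearly agree. The values of r, the SD and the 0.2 SD difference are assumptions.

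The effect is confined to one secondary outcome for which no power is claimed. The primary McNemar analysis and the sample size are unaffected. The point should be fixed, but it does not threaten the main conclusion of the trial.

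**What to change.** In section 8.2, replace the two-group wording with a paired t-test on each patient's Tegaderm-eye score minus EyeGard-eye score, and report the mean difference with its paired 95% confidence interval. The two tape means can still be shown descriptively. A Wilcoxon signed-rank test is an optional alternative, given the short ordinal scale.

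Define the *aggregate* score so that the analysed quantity is one value per eye, consistent with section 8.4.

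The cost is one or two sentences. The per-eye scores and tape assignments are already to be recorded under one subject ID, so no new data, visits or patients are needed.
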